13.4.2. Analysis Window for Consecutive Spot uPCR

P	ar	t	A	+	R	
	al		-	-	P	•

Part	Study visit	Mapped visit	Target day	Analysis window	Interval
Core	3a	Week -4	-28	< -21	NA
Study Phase (Part A)	3b	Week -2	-14	-21 - 0	21
	4	Day 1	1	1	1
	5	Week 2	14	2-<21	19
	6	Week 4	28	21 - <35	14
	6a*	Week 6	42	35 - < 49	14
	7	Week 8	56	49 - < 63	14
	7a	Week 10	70	63 - < 77	14
	8	Week 12	84	77 - < 91	14
	8a	Week 14	98	91 - < 105	14
	9	Week 16	112	105 - < 119	14
	9a	Week 18	126	119 - < 133	14
	10	Week 20	140	133 - < 147	14
	10a	Week 22	154	147 - < 161	14
	11	Week 24	168	161 - < 175	14
	11a	Week 26	182	175 - < 189	14
	11b	Week 28	196	189 - < 203	14
	12	Week 30	210	203 - < 217	14
	12a	Week 32	224	217 - < 231	14
	12b	Week 34	238	231 - < 245	14
	13	Week 36	252	245 - < 259	14
	13a	Week 38	266	259 - < 273	14
	13b	Week 40	280	273 - < 287	14
	14	Week 42	294	287 - < 301	14
	14a	Week 44	308	301 - < 315	14
	14b	Week 46	322	315 - < 329	14
	15	Week 48	336	329 - < 343	14

Part B:

When	Transition	Visits	in	Part A	1:
------	------------	--------	----	--------	----

Part	Study visit	Mapped visit	Target day	Analysis window	Interval
Long-Term Extension Phase	15	Day 1	1	1	1
	15a	Week 6	42	2 - < 63	62
(Part B)	16	Week 12	84	63 - < 105	42
	16a	Week 18	126	105 - < 147	42
	17	Week 24	168	147 - < 189	42
	17a	Week 30	210	189 - < 231	42
	18	Week 36	252	231 - < 273	42
	18a	Week 42	294	273 - < 315	42
	19	Week 48	336	315 - < 357	42
					42

When Transition Visits in Part B:

Part	Study visit	Mapped visit	Target day	Analysis window	Interval
Long-Term	15	Day 1	1	1	1
Extension Phase	T1	Week 1	7	2 - < 11	9
(Part B)	T2	Week 2	14	11 - < 21	10
	T3	Week 4	28	21 - < 35	14
	15a	Week 6	42	35 - < 63	28
	16	Week 12	84	63 - < 105	42
	16a	Week 18	126	105 - < 147	42
	17	Week 24	168	147 - < 189	42
	17a	Week 30	210	189 - < 231	42
	18	Week 36	252	231 - < 273	42
	18a	Week 42	294	273 - < 315	42
	19	Week 48	336	315 - < 357	42
					42

* "a" in Study Visit is added based on schedule of assessment in protocol.

13.4.3. Analysis Window for Other Endpoints

Part	Study visit	Mapped visit	Target day	Analysis window	Interval
Core	3a	Week -4	-28	<-21	NA
Study Phase	3b	Week -2	-14	-21 - 0	21
(Part A)	4	Day 1	1	1	1
	5	Week 2	14	2-<21	19
	6	Week 4	28	21 - < 42	21
	7	Week 8	56	42 - < 70	28
	8	Week 12	84	70 - < 98	28
	9	Week 16	112	98 - < 126	28
	10	Week 20	140	126 - < 154	28
	11	Week 24	168	154 - < 189	35
	12	Week 30	210	189 - < 231	42
F	13	Week 36	252	231 - < 273	42
	14	Week 42	294	273 - < 315	42
	15	Week 48	336	315 - < 343	28

Part A + B:

Part B:

When Transition Visits in Part A:

Part	Study visit	Mapped visit	Target day	Analysis window	Interval
Long-Term	15	Day 1	1	1	1
Extension	16	Week 12	84	2 - < 126	125
(Part B)	17	Week 24	168	126 - < 210	84
	18	Week 36	252	210 - < 294	84
	19	Week 48	336	294 - < 378	84
					84

Part	Study visit	Mapped visit	Target day	Analysis window	Interval
Long-Term	15	Day 1	1	1	1
Extension Phase	T1	Week 1	7	2 - < 11	10
(Part B)	T2	Week 2	14	11 - < 21	10
	T3	Week 4	28	21 - < 56	35
	16	Week 12	84	56 - < 126	70
	17	Week 24	168	126 - < 210	84
	18	Week 36	252	210 - < 294	84
	19	Week 48	336	294 - < 378	84
					84

When Transition Visits in Part B:

13.5. Repeated or Unscheduled Assessments of Safety Parameters

For safety parameters, if a subject has repeated assessments before the start of investigational product, then the results from the final assessment made prior to the start of investigational product will be used as baseline. If end of study assessments is repeated or unscheduled, the last post-baseline assessment will be used as the end of study assessment for generating descriptive statistics. However, all post-baseline assessments will be used for Potentially Clinically Significant (PCS) value determination and all assessments will be presented in the data listings.

13.6. Handling of Missing, Unused, and Spurious Data

13.6.1. Missing Date of Investigational Product

When the date of the last dose of investigational product is missing for a subject in the Safety Set, all efforts should be made to obtain the date from the investigator. If it is still missing after all efforts, then the last visit date will be used in the calculation of treatment duration.

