### **13.4.** Follow-up (Visits 16-20)

All subjects who complete study treatment through Day 336/Week 48 but do not enter the Part B Long-Term Extension Phase will need to return to the clinical site for Follow-up Visits 16, 17, 18, 19, and 20, where the assessments outlined in the schedule of events (Section 4) will be performed.

Subjects who discontinue treatment early and do not continue their participation in the study should complete a follow-up visit 6 weeks after discontinuation of treatment and also the Exit Visit 6 weeks thereafter.

Visit window:  $\pm 2$  days (Visits 16-18)  $\pm 7$  days (Visits 19 and 20)

- Procure 3 previously collected consecutive uPCR samples to site (Visits 16-20)
  - Arrange courier pickup for all biweekly triplicate uPCR samples during non-clinic visit weeks
- Physical examination (Visit 16 and 17 only)
- Concomitant medications review (Visit 16 and 17 only)
- Injection Site Assessment (Visit 16 only)
- Antidrug Ab collection
- eGFR assessment
- Urinalysis collection (See schedule of events for details)
- Urine pregnancy test (Visit 16-19 only)
- AE review
- PK Sample collection
- Vital Signs
- Blood tests (See schedule of events for details)
- Triplicate 12-lead ECG
- Dispense uPCR containers for consecutive collection (Visits 16-20):
  - 3 uPCR containers (Visits 16 and 17), 6 uPCR containers (Visit 20), 9 uPCR containers (Visits 18 and 19)
- Dispense 24-hour urine container

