Visit Window (±Days)	2	2	2	2	7	7	7	NA
$Pegceta coplan\ administration^{b,f}$	X	X	X	X	X	X	X	
Injection site assessment g	X	X	X	X	X	X	Х	
Concomitant medications	X	X	X	X	X	X	Х	X
Vital sign measurementsh	X	X	X	X	X	X	Х	X
Urine								
24-hour Urine Collection i	X					Xi	Xi	X
Dispense uPCR containers	X		X	X	X	X	Х	
Return uPCR samples j			X	X	X	X	Х	
Urinalysis—microscopic & Dipstick k	Х	Х	X	Х	X	Х	х	Х
Blood 								
Pharmacokinetic Sample Collection m	Х	Х	Х	Х	X	Х	х	Х
Antidrug Ab assays n	X			X		Х	X n	X
Hematology and chemistry 0,p	X	X	X	X	X	X	Х	X
PD for Complement profile	X	X	X	X	X	X	Х	X
Pregnancy (β-HCG and FSH)	X							
Disease-Specific Biomarkers	X							X
eGFR q	X							X
Urine pregnancy test r	X			X	X	X	Х	
Adverse events	X	X	X	X	X	X	х	Х
Drug Dispensation for Home Administration	X	Х	Х	Х	X	Х	Х	

Abbreviations: Ab = antibodies; ACR = albumin-to-creatinine ratio; ADA = antidrug antibody; ALP = alkaline phosphatase; ALT = alanine aminotransferase; aPTT = fibrinogen activated partial thromboplastin time; AST = aspartate aminotransferase; β-HCG = beta human chorionic gonadotropin; BUN = blood urea nitrogen; CKD-EPI = Chronic Kidney Disease Epidemiology Collaboration; ECG = electrocardiogram; eGFR = estimated glomerular filtration rate; ETE = Early Termination Exit Visit; ETF = Early Termination Follow-up Visit; FSH = follicle-stimulating hormone; GGT = gamma-glutamyl transferase; INR = international normalized ratio; LDH = lactate dehydrogenase; PCR = protein-to-creatinine ratio; PD = pharmacodynamics; PI = primary investigator; PK = pharmacokinetics; RBC = red blood cell(s); SC = subcutaneous;

uACR = urine albumin-to-creatinine ratio; uPCR = urine protein-to-creatinine ratio; WBC = white blood cell(s); WOCBP = women of childbearing potential.

- a Subjects who discontinue treatment early should complete one ETF 6 weeks after discontinuation of treatment and one ETE Visit 6 weeks after the ETF.
- b If subjects have not transitioned to twice-weekly dosing before entry into Part B, then transition visits T1, T2, and T3 need to be scheduled. Patients who had transitioned to twice-weekly dosing prior to entry into Part B may omit the Part B dose transition visits.

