# A1.1.2. Part B Long-Term Extension Phase: Study Design and Procedures

Following Visit 15 (Week 48), subjects who elect to continue in Part B, the Long-Term Extension Phase, will return to the site at 12-week intervals until pegcetacoplan is commercially available for the disease under treatment.

Specific procedures for each visit are listed in the Study Flow Chart for the Long-Term Extension Phase in Table A1.

The vaccination history for each subject should be reviewed prior to entry into the Long-Term Extension Phase, and any additional vaccinations or boosters against *N. meningitidis*, *S. pneumoniae*, or *H. influenzae* as recommended in the Advisory Committee on Immunization

Practices (ACIP) guidelines for patients with immunocompromising conditions (available at https://www.cdc.gov/vaccines/schedules/hcp/imz/adult-conditions.html) should be provided. If additional vaccinations or boosters are required, vaccination titer samples should be collected before administration of the vaccination and at the next scheduled visit.

At Visit 15 (Week 48), subjects who are invited to participate in Part B, the Long-Term Extension Phase who have not already transitioned to 1080 mg twice-weekly pegcetacoplan treatment during Part A, will begin a pegcetacoplan dose regimen of pegcetacoplan 1080 mg twice weekly (with potential to escalate to pegcetacoplan 1080 mg every 3 days). Subjects should follow the Dose Transition visits as outlined in Table A1.

If a subject will initiate the pegcetacoplan 1080 mg twice weekly dose regimen at Visit 15, he or she should be instructed to skip their daily Part A Core Study Phase Dose the day prior to Visit 15 (ie, the subject should not self-administer pegcetacoplan on Day 335).

Subjects who discontinue treatment early should complete an Early Termination Follow-up Visit 6 weeks after discontinuation of treatment, and an Early Termination Exit Visit 6 weeks later as outlined in Table A1.

Study Assessments align with those conducted in the Core Study Phase and are described in Section 14.1.

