5.5. Exposure to Study Drug

The following parameters will be calculated and presented by disease group for Part B and Part A + B using the Safety Population:

- Total dose administered (mg)
- Duration of APL-2 dosing (days) (overall) defined as (last infusion date first infusion date + 1)
- Duration of APL-2 dosing (days) for the 360 mg daily group / 1080 mg twice weekly group / 1080 mg every 3 days group defined as the sum of each period of the respective dosing group.
- Number and percentage of subjects who received at least one infusion
 - o Number and percentage of subjects with all planned infusions administered
 - o Number and percentage of planned bi-weekly infusions administered
 - Number and percentage of planned daily infusions administered
 - Number and percentage of subjects with any infusions missed
 - Number and percentage of subjects with one or more incomplete infusions
 - Number and percentage of subjects with all infusions administered as prescribed

If the investigator instructed the subject to stop taking study medication for a period of time, e.g. due to an adverse event, then this period will not be included in the denominator for the exposure calculation.

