7.1. Adverse Events

Adverse events (AEs) will be coded using the most recent version of MedDRA.

Severity of AEs will be assessed and classified into mild, moderate, severe, life-threatening or death by investigators. Handling rules for missing severity of AEs are described in Section 13.6.4.

Treatment emergent adverse events (TEAEs) are defined as those AEs that develop or worsen after the first dose of study medication and up to 56 days beyond the last dose of study drug.

AEs are classified as related if AEs are definitely related, probably related or possibly related to study drug; Any AEs with missing or unknown relationship will be considered as related to study drug.

All summaries of AEs described in this section will be on TEAEs. All summaries will be ordered by decreasing frequency of number of subjects in PT within SOC. In the case of equal frequency of number of subjects in SOCs or PTs, then summaries of AEs will be sorted alphabetically.

All summary tables will be presented for Part B and Part A + B, where AEs will be categorized by the Part in which the AE started, i.e. an AE which began during the Part A will be categorized under Part A even if it continues into Part B.

An overall summary for AEs including number of subjects who experience a TEAE, number of total TEAEs and number of unique TEAEs will be provided:

- TEAE
- APL-2-related TEAE
 - Related
 - Not related
- Infusion-related TEAEs
 - Related
 - Not related

- Serious TEAE
- Maximum severity of TEAEs
- Infusion site reaction (yes/no)
- TEAE leading to APL-2 withdrawn
- TEAE leading to dose interruption
- TEAE leading to death

The following summary will be provided by disease group for Part B and Part A + B:

- TEAEs by SOC and PT
- APL-2 Related TEAEs by SOC and PT
- Infusion-Related TEAEs by SOC and PT
- Serious TEAEs by SOC and PT
- TEAE by SOC, PT and maximum severity
- TEAE leading to APL-2 discontinuation by SOC and PT
- TEAE leading to dose interruption by SOC and PT
- TEAE leading to death by SOC and PT

If a SOC or PT was reported more than once for a subject, the subject would only be counted once in the incidence for that SOC or PT.

For subjects experiencing the same PT at multiple severities, the occurrence of the AEs with the greatest severity will be used in the analysis of incidence by severity.

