13.6.2.2. Incomplete Stop Date

The following rules will be applied to impute the missing numerical fields. If the date of the last dose of investigational product is missing, then replace it with the last visit date. If the imputed stop date is before the start date (imputed or non-imputed start date), then the imputed stop date will be equal to the start date.

- Missing Day and Month
 - If the year of the incomplete stop date is the same as the year as of the date of the last dose of investigational product, then the day and month of the date of the last dose of investigational product will be assigned to the missing fields.
 - If the year of the incomplete stop date is before the year of the date of the last dose of investigational product, then 31 December will be assigned to the missing fields.
 - If the year of the incomplete stop date is after the year of the date of the last dose of investigational product, then 01 January will be assigned to the missing fields.
- Missing Month Only
 - The day will be treated as missing and both month and day will be replaced according to the above procedure.
- Missing Day Only
 - If the month and year of the incomplete stop date are the same as the month and year of the date of the last dose of investigational product, then the day of the date of the last dose of investigational product will be assigned to the missing day.
 - If either the year is before the year of the date of the last dose of investigational product or if both years are the same but the month is before the month of the date of the last dose of investigational product, then the last day of the month will be assigned to the missing day.
 - If either the year is after the year of the last dose of investigational product or if both years are the same but the month is after the month of the date of the last dose of investigational product, then the first day of the month will be assigned to the missing day.

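### The SAP replaces a missing last-dose date with the last visit date without excluding post-treatment visits, so dosing duration can be overstated by 42 or 84 days in a Part B early stopper

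*SAP*

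**What the plan says.** SAP 13.6.1 applies to subjects in the Safety Set whose last-dose date is missing. The site is queried first: "all efforts should be made to obtain the date from the investigator". If that fails, the rule is: "If it is still missing after all efforts, then the last visit date will be used in the calculation of treatment duration".

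SAP 13.6.2.2, on incomplete medication stop dates, uses the same device: "If the date of the last dose of investigational product is missing, then replace it with the last visit date". SAP 13.6.3 applies the 13.6.2.2 rules to adverse-event stop dates where these are imputed.

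SAP 5.5 defines overall duration of dosing as last infusion date minus first infusion date plus 1. (The minus sign is lost in the extracted text and is read in here.)

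SAP 4.2 limits the Safety Set to subjects who roll over into Part B and receive at least one 1080 mg dose, so the Part B visit schedule governs. Footnote a of protocol Table A1 reads: "Subjects who discontinue treatment early should complete one ETF 6 weeks after discontinuation of treatment and one ETE Visit 6 weeks after the ETF". Protocol A1.1.2 agrees, asking for the early-termination follow-up visit and then "an Early Termination Exit Visit 6 weeks later as outlined in Table A1". Protocol 13.4 has the same 6 + 6 week pattern for Part A subjects who stop and leave the study, but subjects who never enter Part B are outside this SAP's Safety Set.

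**The concern.** The last visit date is a sensible stand-in for the last dose when a subject is lost while still dosing. It is a poor one for a subject who stops and then attends follow-up as the protocol asks, because that subject's last visit is scheduled to fall off drug. The rule as written does not separate the two cases.

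What is at stake is the exposure summary. Among early stoppers who attend these visits the error always lengthens duration. The disease groups are also small: 6 to 12 per disease were planned for Part A, and only those who roll over are counted here.

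**Working it through.** The documents give no treatment-duration figure to reproduce, so this is date arithmetic on the stated rules.

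**Inputs**
- Substituted date: last visit, of any kind (SAP 13.6.1, 13.6.2.2).
- ETF: 6 weeks after stopping, 6 × 7 = 42 days. ETE: 6 weeks later, 42 + 42 = 84 days (protocol Table A1 footnote a; A1.1.2).
- Duration = last infusion − first infusion + 1 (SAP 5.5). An error of *d* days in the last date is an error of *d* days in duration.
- Assumptions: the visits occur on schedule, and treatment discontinuation coincides with the last dose. The stopping times below are illustrative.

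**Part B duration**

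| True stop (Part B) | True days | Last visit = ETF (+42) | Last visit = ETE (+84) |
|---|---|---|---|
| Week 4 | 28 | 70 (+150%) | 112 (+300%) |
| Week 12 | 84 | 126 (+50%) | 168 (+100%) |
| Week 24 | 168 | 210 (+25%) | 252 (+50%) |
| Week 48 | 336 | 378 (+12.5%) | 420 (+25%) |
| Week 72 | 504 | 546 (+8.3%) | 588 (+16.7%) |

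**Part A + B duration.** Part B starts at Day 336, so Part A adds 335 days. For a Week 12 stop, 335 + 84 = 419 days becomes 419 + 84 = 503 (+20.0%). For a Week 48 stop, 671 becomes 755 (+12.5%).

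**Effect on a group mean.** One affected subject at +84 days moves the mean by 84/n: 14 days at n = 6 and 7 days at n = 12. The number entering Part B per disease is not stated. If it is below 6, the shift is larger.

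**Does anything else remove these days?** The exclusion in SAP 5.5 covers periods when the investigator told the subject to pause. It adjusts the exposure denominator and does not change the last-dose date. No other SAP section bars ETF or ETE visits from serving as the last visit.

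**The case against.** The strongest reply is that the two conditions rarely coexist. The date must stay unknown after a site query, yet the subject must have attended visits that are timed from the end of treatment. A site that scheduled those visits knew roughly when treatment stopped, and it saw the subject again and could ask. The protocol also requires prompt notice to the medical monitor (13.5), a Part B diary entry for each dose (A1.1.4.2), an infusion log (A1.1.5.4) and return of used and unused product at each visit (12.5). A permanently unknown date is likelier in someone lost to follow-up, who has no ETF or ETE. All of this stands. It limits how often the error occurs, but it does not make the rule right when it does.

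A reader might infer three larger consequences. The documents do not support them.

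- *Adverse events per unit of time on drug would look lower.* SAP 7.1 plans counts of subjects and events. No exposure-adjusted rate is planned, so duration is not a denominator for any adverse-event summary.
- *The treatment-emergent window would run to 84 + 56 = 140 days after the true last dose.* SAP 7.1 sets the limit at "up to 56 days beyond the last dose of study drug", but SAP 13.6.1 confines the substitution to treatment duration, and nothing carries it into that definition. Even if it were carried over, protocol 15.2 ends routine collection at the exit or early-termination visit, about day 84. The extra interval would be about 84 − 56 = 28 days, apart from suspected-related serious events reported later.
- *Event and medication durations would be materially distorted.* Adverse-event stop dates are imputed only where the protocol requires an event duration, and SAP 7.1 plans no such summary. For medications, both the stop date and the last-dose date would have to be deficient.

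The compliance formulas in SAP 5.6 also use the last dose date, but 13.6.1 does not extend to them, so no effect is claimed there.

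**Conclusion.** The point holds as a minor flaw in one descriptive exposure summary. An affected Part B early stopper has dosing duration overstated by 42 days if only the ETF is attended, or 84 days if the ETE is attended too. This assumes that the visits are on schedule and that the last-dose date stays missing after query. The documents give no count of such subjects, and it may be zero. A subject lost while dosing is not affected in this way. No efficacy result and no planned adverse-event rate depends on the rule. It is worth correcting because better dates should already exist and the correction is cheap.

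**What to change.** Replace the substitution sentence in both SAP 13.6.1 and SAP 13.6.2.2 with:

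> Use the last dose documented in the dosing diary or drug accountability record; if none, the recorded treatment-discontinuation date; if that is also missing, the last on-treatment visit date. ETF, ETE and other post-treatment follow-up visits are not used.

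The order matters. Taking the earlier of the discontinuation date and the last on-treatment visit would create a new error, because Part B visits are 12 weeks apart (protocol A1.1.2) and dosing continues at home between them. For example, a subject who stopped 77 days after a visit would have a recorded discontinuation date overridden by one 77 days too early.

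For the same reason, add that the visit fallback must not shorten the 56-day treatment-emergent window. In that example a window anchored on the visit would close 77 − 56 = 21 days before the true last dose and drop on-treatment events. When the last dose is known only from the visit fallback, count adverse events of uncertain timing as treatment-emergent, in line with SAP 13.6.3.

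The cost is two replaced sentences and one added. No new data are needed for the first step, since diaries and accountability records are already required. The documents do not say in which field the discontinuation date is captured, but the ETF timing and the treatment-discontinuation cut-off in SAP 6.3 both presuppose one. The SAP should name that field.

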13.6.2. Missing Dates Information for Prior or Concomitant Medications

For the purposes of determining prior and concomitant medications, if a partial date is recorded, the following convention will be used to assign the medication dates:

- If a start date is missing the day information and month/year is the same as first dose date then use first dose date, else '01' will be used for the day; if a start date is missing the month and the year is the same as first dose date then use first dose date, else January will be used for the start month.
- If a stop date is missing the day information and month/year is same as last study date then use last study date, else last day of the given month will be used for the stop day; if a stop date is missing the month and year is the same as last study date then use last study date, else December will be used for the stop month.

